## 7.3 FOLLOW-UP PROCEDURES

### 7.3.1 IMMEDIATELY POST-PROCEDURE

All subjects will be required to wear a Sponsor-provided compression vest for 2-3 weeks.

### 7.3.2 FOLLOW-UP VISITS & SUBJECT CONTACT OUTSIDE OF FOLLOW-UP VISITS

Investigators will follow-up with the study subjects, per their Standard of Care (SOC), at the following time-points:

- 30 ( $\pm 7$ ) days,
- 90 ( $\pm 10$ ) days, and
- 180 ( $\pm 15$ ) days.

**TABLE 3: STUDY REQUIRED PROCEDURES**

	Baseline/ Pre-Procedure Screening 	Procedure (Day 0)	30 Days	90 Days	180 Days
			23-37 days	80-100 days	165-195 days
Informed Consent	X				
Assess Inclusion/Exclusion Criteria	X				
Medical History	X				
General Physical Exam	X				
Review Medications	X		X	X	X
Patient Treatment Survey	X				
Imaging (front, lateral, and oblique) 	X		X	X	X
Gynecomastia Grade	X		X	X	X
STPTUP	X	X	X	X	X
STPTIMF	X	X	X	X	X
Chest Measurements	X	X	X	X	X
Study Procedure		X			
Adverse Event Assessment		X	X	X	X
Modified Global Aesthetic Improvement Scale (GAIS) 			X	X	X
Subject Satisfaction Survey					X

 Pre-procedure Screening assessments to take place within 30 days prior to undergoing the procedure.

 To be completed by Investigator and study subject at day 30, day 90 and day 180 follow-up visits.

 Images used for IPR Assessment.

#### 7.4 SUBJECT RANDOMIZATION AND TREATMENT GROUP ASSIGNMENT

All subjects will be treated per standard of care.). They will be blinded as to which side of the chest is receiving Renuvion.

## 7.5 STUDY SCHEDULE

### 7.5.1 SCREENING

- Obtain informed consent of potential participant verified by signature on study informed consent form.
- Verify all preliminary/screening inclusion/exclusion criteria are met.

### 7.5.2 BASELINE ASSESSMENT

- Obtain protocol-required baseline measures
- Document medical history.
- Perform baseline photography
- Document concurrent medications.
- Obtain height and weight.

### 7.5.3 TREATMENT VISIT

- Greater than 30 days between baseline and treatment visits will require that the subject be re-screened to confirm enrollment eligibility.
- Perform study treatment.

### 7.5.4 FOLLOW-UP

Subjects will be asked to return to the clinic for in-person follow-up visits at 30, 90, and 180 days post-treatment. At all visits, subjects will be assessed for safety and efficacy, images will be taken, adverse events and protocol deviations will be assessed, and study outcome measures (Gynecomastia Grade, STPTUP, STPTIMF, GAIS) will be completed. At the 180-day follow-up appointment in addition to the above referenced assessments, the subject will complete a Patient Satisfaction Questionnaire. Following study participation, the subject will be offered an optional balancing treatment to the side not previously treated with Renuvion. Virtual visits are not allowed for D30, D90, and D180 as images and measurements are required that are not able to be completed virtually.

### 7.5.5 SAFETY ASSESSMENTS

Adverse events will be assessed immediately post-treatment and at all follow-up visits.

### 7.5.6 UNSCHEDULED VISITS

Investigators may see subjects for visits in addition to the Day 30, Day 90, and D180 at their discretion. Any unscheduled visit or examination should be documented in the subject's medical record and adverse event form (if applicable) stating the reason for the visit and any actions taken. The Sponsor should be notified of the unscheduled visit.

### 7.5.7 END OF STUDY (COMPLETION)

All subjects who have signed an Informed Consent Form will be considered enrolled in the study. Subjects who complete the study duration will be considered to have completed the study. The end of study will be defined as completion of all study visits by all enrolled subjects. If a device-related AE, SAE, or unanticipated serious device-related effect is ongoing at the final study visit, the subject will be followed until resolution, until the condition stabilizes, until the event is otherwise explained, or the subject is lost to follow-up.

A study closure visit may be conducted at the study site to review record retention requirements, device disposition requirements, etc., with site personnel. The Sponsor may choose to conduct the closure visit via telephone contact or online conference if appropriate.

## 8. ASSESSMENT OF SAFETY

### 8.1 SPECIFICATIONS OF SAFETY PARAMETERS

#### 8.1.1 DEFINITION OF AN EXPECTED TREATMENT EFFECT (ETE) AND AN ADVERSE EVENT (AE)

An expected treatment effect is defined as any typical treatment side-effect of Renuvion APR System of mild to moderate severity and lasting up to a typical maximum duration. An adverse event is defined as any new medical problem, or exacerbation of an existing problem, experienced by a subject while enrolled in the study, whether or not it is considered device-related by the investigator.

A preexisting condition (one that is present at the start of the study) will be recorded as an AE only if the frequency, intensity, or the character of the condition worsens during the study period. Neither the condition, hospitalization, prolonged hospitalization, nor surgery are reported as an AE in the following circumstances: hospitalization or prolonged hospitalization for diagnostic or elective surgical procedures for a preexisting condition. Surgery should not be reported as an outcome of an AE if the purpose of the surgery was elective or diagnostic and the outcome was uneventful.

All ETEs and AEs will be collected during the conduct of this trial.

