Exclusion Criteria:	
 
1. Subjects without clinical diagnosis of primary Gynecomastia and/or a clinical diagnosis of gynecomastia with secondary causes such as medications, drugs, or testicular tumors.
 
2. Subjects presenting with ASA Physical Status Classification System Classes III or higher.
 
3. Gynecomastia Rohrich Grade I.
 
4. Non-symmetrical gynecomastia Rohrich grades.
 
5. Non-symmetrical chest measurements (more than 3% variance between sides).
 
6. Previous treatment or surgery in the breast area.
 
7. Active systemic or local skin disease that may alter wound healing.
 
8. Significant or uncontrolled medical condition that in the opinion of the investigator participation in the study may compromise the patient's health.
 
9. History of autoimmune disease (excluding Hashimoto's thyroiditis).
 
10. Known susceptibility to keloid formation or hypertrophic scarring.
 
11. Cancerous or pre-cancerous lesions in the area to be treated.
 
12. Possesses a surgically implanted electronic device (i.e. pacemaker).
 
13. Serious mental health illness such as dementia or schizophrenia; psychiatric hospitalization in the past two years.
 
14. Use of endermology post-procedure for the duration of the study.
 
15. Participation in any other investigational study within 30 days prior to consent and throughout study participation.
 
16. Subject who, in the opinion of the investigator, is not an appropriate candidate for the study.
 

Primary Safety Endpoint:	Analysis of bilateral occurrence of adverse events (both sides).
Outcome Measures:	
 
1. Bilateral analysis of change to STPTUP (Tebbetts & Adams High 5 Measurements) from baseline to day 30, 90, and 180.
 
2. Bilateral analysis of change to STPTIMF (Tebbetts & Adams High 5 Measurements) from baseline to day 30, 90, and 180.
 
3. Bilateral analysis of male chest measurements (Murphy) from baseline to day 30, 90, and 180.
 
4. Bilateral analysis of skin excised during the procedure by Gynecomastia Grade (Rohrich Classification).
 

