#### **4.3 STUDY ENDPOINTS**

##### **4.3.1 PRIMARY SAFETY ENDPOINT**

The primary safety endpoint is the bilateral occurrence of adverse events.

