#### 4.3.3.8 ADVERSE EVENT REPORTING

The definitions of Adverse Events (AEs) and the subtypes are provided in **Section 8** of this study protocol. Adverse events will be classified by the investigator as to:

- Anticipated vs unanticipated
- Serious vs not serious
- Expected Treatment Effect (ETE) vs Adverse Event (AE)
- Severity: mild, moderate, severe
- Device causality: not related, related, undetermined
- Procedure causality: not related, related, undetermined.

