### 8.3 TIME PERIOD AND FREQUENCY FOR EVENT ASSESSMENT AND FOLLOW-UP

The occurrence of an AE or SAE may come to the attention of study personnel during a study visit or upon review by a study monitor. All ETEs and AEs will be captured on the appropriate CRF. Information to be collected includes event description, date of onset, clinician's assessment of seriousness and severity, relationship to study device/treatment (assessed only by those with the training and authority to make a determination), actions taken, and date of event resolution. All AEs occurring while on study must be documented appropriately regardless of relationship.

A pre-existing condition should not be reported as an adverse event unless there has been a substantial increase in severity or frequency of the problem that has not been attributed to natural history. Changes in the severity of an event will be documented to allow for a determination if the event should be re-categorized from an ETE to AE.

Safety evaluations for this study include an interview with the study subject at each follow-up visit by the Investigator or delegated study staff to elicit information about any medical occurrence that meets the definition of Adverse Event. This information will be documented in CRF without regard for cause or relation to device and/or procedure.

In addition, study subjects will be instructed in the Informed Consent Form, post-procedure take-home instructions, and verbally by study staff to report all complications experienced post study procedure to the site personnel as soon as they occur/are observed. Study staff will ensure that monitoring and management of all adverse events is prioritized.

Study investigators are provided liberty to mitigate adverse events as deemed necessary per IHC GCP Guidelines E6(R2)4.3.2 which states "During and following a subject's participation in a trial, the investigator/institution should ensure that adequate medical care is provided to a subject for any adverse events related to the trial".

Adverse event resolution dates will be determined by investigator using either in-person or remote (phone, video call, text, email, etc.) examinations or communication with the subject. To ensure the most accurate reporting of adverse event durations, investigators are instructed not to wait until scheduled office follow-up visits to assess resolution.

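### The protocol does not fix whether an expected treatment effect counts as an adverse event in the primary safety endpoint, and one possible reading labels the same effect differently on the two sides of the chest

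*Protocol*

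**What the plan says.** Section 4.3.1 of the Protocol states: "The primary safety endpoint is the bilateral occurrence of adverse events". The Synopsis says the same and adds that both sides are meant. Neither place mentions ETEs.

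The definitions and classification rules are spread over several sections:

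- **Section 8.1.1, ETE:** "An expected treatment effect is defined as any typical treatment side-effect of Renuvion APR System of mild to moderate severity", lasting no longer than a maximum that is called typical but is given no value.
- **Section 8.1.1, AE:** "any new medical problem, or exacerbation of an existing problem, experienced by a subject while enrolled in the study", related to the device or not. ETEs are not excepted. The section adds that both kinds of event are collected.
- **Section 4.3.3.8:** "The definitions of Adverse Events (AEs) and the subtypes are provided in" Section 8. The investigator then classifies adverse events on several axes, one of which is "Expected Treatment Effect (ETE) vs Adverse Event (AE").
- **Section 8.3:** changes in severity are documented "to allow for a determination if the event should be re-categorized from an ETE to AE".
- **Section 2.2.1:** the list of common ETEs includes pain, edema and temporary sensory nerve injury.
- **Section 8.2.2:** edema, hematoma, nerve injury and pain, as events known from such procedures without the device, go down as procedure related.
- **Section 7.2:** Renuvion is applied to one side only, and subjects do not know which.

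On timing, Section 8.3 records events from consent until 7 days (non-serious AEs) or 30 days (SAEs) after participation ends. The first paragraph of Section 8.4.1 runs from first exposure to the last follow-up visit. Its last paragraph takes signing of consent as the starting point.

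**The concern.** Each subject is his own control, so the safety comparison is side against side. It is informative only if the same event receives the same label on either side.

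The ETE definition refers to the Renuvion system, and one side never receives it. If ETE and AE are alternatives, and an ETE can arise only where Renuvion was used, a mild listed effect leaves the AE count on the treated side and stays in it on the other. The treated side would then look safer because of the labels alone.

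The investigator assigns the label and is not described as blinded to side; the subjects and the independent photographic reviewers are. With up to 3 sites, different codings could also meet in one table. Labels are assigned at the site from the Protocol's definitions, so a later choice of tables cannot fully repair AE-only counts.

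**Working it through.** **Step 1. Is an ETE a kind of AE?** The AE definition in Section 8.1.1 covers any new medical problem, so an ETE that is one also meets it. The lead-in to the list in Section 4.3.3.8 agrees, because what is being classified is already an adverse event. The ETE/AE item in that list, and the re-categorization in Section 8.3, make the two mutually exclusive. Section 4.3.3.8 thus supports both positions by itself.

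**Step 2. What does each reading do by side?** Take a mild effect that is listed in Section 2.2.1 and also named in Section 8.2.2, such as edema or pain.

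| Reading | Renuvion side | Surgery-only side | By side |
|---|---|---|---|
| A. ETE is a kind of AE | counted | counted | neutral |
| B. ETE is a type of effect, wherever it occurs | ETE, set apart | ETE, set apart | neutral |
| C. ETE needs attribution to Renuvion, with Section 8.2.2 applied to both sides | AE | AE | neutral |
| D. ETE only where Renuvion was used, otherwise AE | ETE, set apart | AE | favours the device |

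Events that Section 2.2.1 lists as risks beyond the ETEs (burns, seroma, hematoma) are AEs on either side under all four readings.

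**Step 3. Illustration of size.** The Protocol gives no event rates, so the rates here are assumptions. Inputs: n = 10 (Section 10.2, the maximum); p = per-side rate of listed mild or moderate effects, equal on both sides, at 0.3, 0.5 or 0.8; u = per-side rate of unlisted events, independent of p, at 0 or 0.2.

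Reading D:
- Renuvion side: 10u
- Surgery-only side: 10[1 − (1 − p)(1 − u)]
- Gap: 10p(1 − u)

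| Expected sides with an AE | p = 0.3 | p = 0.5 | p = 0.8 |
|---|---|---|---|
| D, u = 0 | 0 v 3 | 0 v 5 | 0 v 8 |
| D, u = 0.2 | 2 v 4.4 | 2 v 6 | 2 v 8.4 |
| Gap, u = 0.2 | 2.4 | 4 | 6.4 |
| A, u = 0.2 | 4.4 v 4.4 | 6 v 6 | 8.4 v 8.4 |
| B, u = 0.2 | 2 v 2 | 2 v 2 | 2 v 2 |

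If only half of the listed Renuvion-side effects are coded as ETEs, with u = 0, the gap is 10 × 0.5 × p = 1.5, 2.5 or 4.

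The level also depends on the reading. In the extreme case where all 10 subjects have one listed effect on a side and nothing else, A gives 10/10 and B gives 0/10. The exact 95% limits follow from 0.025^(1/10) = 0.692: 69.2% to 100% under A, and 0% to 30.8% under B.

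**Step 4. Recording window.** Assume consent 30 days before Day 0 (the limit for screening in Section 7.1), a last visit on Day 180, and participation ending at that visit.

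- Section 8.4.1, first paragraph: 180 days.
- Section 8.3, non-serious AEs: 30 + 180 + 7 = 217 days, which is 37 more.
- Section 8.3, SAEs: 30 + 180 + 30 = 240 days, which is 60 more.

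If Section 8.4.1 is taken to start at consent, as its last paragraph suggests, only the tails of 7 and 30 days remain.

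**The case against.** The strongest case against is that no section instructs reading D. It needs ETE to mean a type of effect on one side and an attribution on the other. Section 8.2.2 does not limit its instruction by side, so a site that follows it would treat edema and pain alike on both. This stands. A reader might infer that the primary endpoint is biased towards the device, and the documents do not support that. They permit such a coding and do not prescribe it.

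It can also be said that the Protocol really means two separate categories, and that the subtypes mentioned in Section 4.3.3.8 may be SAEs and unanticipated device effects. That is plausible. But the AE definition still has no exception, and separate categories alone do not exclude reading D. Two further texts add little either way: the Synopsis names ETEs and AEs separately, and the follow-up rule appears without ETEs in Section 7.5.7 and with them in Section 8.4.1. AEs and SAEs are also named side by side.

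The study is a descriptive pilot with no test on AEs, and both kinds of event are collected. So no error rate is affected, and the combined AE plus ETE count by side can be recovered if side is recorded. Section 8.3 begins "Information to be collected includes event description, date of onset" and does not name side among its items. The CRF is not shown and may already hold it, so this is a point to check and not a defect.

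On the windows, a reader might infer that the texts cannot all be followed. That is too strong: Section 8.4.1 says what will be recorded in its period and does not forbid more, and it returns to consent itself.

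**Conclusion.** The point holds in a conditional form. The Protocol leaves open whether ETEs count in its primary safety endpoint, and it ties the ETE definition to a device used on one side only. Of the four readings, three are side-neutral and one favours the device.

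The possible artefact ranges from none to most of the by-side difference in mild and moderate listed effects. The gaps of 3, 5 or 8 sides out of 10 rest wholly on assumed equal rates, no unlisted events and reading D applied throughout; they are not a forecast. Unlisted events are unaffected.

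This should be fixed before sites code events, because the study's purpose (Section 3) includes informing a possible pivotal study and AE-only counts could not be fully corrected later. The window discrepancy is minor and acts mostly alike on both sides.

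**What to change.** - Reconcile Sections 4.3.3.8, 8.1.1 and 8.3, together with 2.2.1 and 8.2.2, so that ETE and AE are defined and coded by the same rule on both sides. Any side-neutral rule removes the artefact.
- State the maximum duration to which the ETE definition refers.
- Report, per side, the occurrence of all local events (AE plus ETE), with AE-only and ETE-only breakdowns. This also keeps a true excess of listed effects on the Renuvion side visible, which setting ETEs apart on both sides would hide from the AE count.
- Make sure the side of each event is recorded, if the CRF does not already do so.
- Bring the recording windows in Sections 8.3 and 8.4.1 to one start and one end for the endpoint, and list events outside it separately.

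The cost is Protocol wording and at most one CRF field, since ETEs, AEs and onset dates are already collected. The drawback is that headline event counts rise once ETEs are included.

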#### 8.1.2 DEFINITION OF SERIOUS ADVERSE EVENT (SAE)

Each adverse event should be assessed for its seriousness. The definition below should be used for this assessment. Please note that the term serious adverse event is not synonymous with a "severe" adverse event, which may be used to describe the intensity of an event experienced by the subject.

An adverse event should be classified as serious if it meets any of the following criteria:

- a. Death  
Death was an outcome of the adverse event.
- b. Life-threatening  
The subject was at substantial risk of dying at the time of the adverse event or use or continued use of the device.
- c. Hospitalization (initial or prolonged)  
Admission to the hospital or prolongation of hospitalization was a result of the adverse event.
- d. Disability or Permanent Damage  
The adverse event resulted in a substantial disruption of a person's ability to conduct normal life functions, i.e., the adverse event resulted in a significant, persistent or permanent change, impairment, damage or disruption in the patient's body function/structure, physical activities and/or quality of life.
- e. Congenital Anomaly/Birth Defect  
Exposure to a medical product prior to conception or during pregnancy may have resulted in an adverse outcome in the child.
- f. Required Intervention to Prevent Permanent Impairment or Damage (Devices)  
Medical or surgical intervention was necessary to preclude permanent impairment of a body function, or prevent permanent damage to a body structure, either situation suspected to be due to the use of a medical product.
- g. Other Serious (Important Medical Events)  
The event does not fit the other outcomes, but the event may jeopardize the subject and may require medical or surgical intervention (treatment) to prevent one of the other outcomes.

Non-serious adverse events are all events that do not meet the criteria for a “serious” adverse event.

#### 8.1.3 DEFINITION OF UNANTICIPATED ADVERSE DEVICE EFFECTS (EVENTS)

An unanticipated adverse device effect is defined as “any serious adverse effect on health or safety, or any life-threatening problem, or death caused by, or associated with, a device; if that effect, problem, or death was not previously identified in nature, severity, or degree of incidence in the investigational plan, or application (including supplementary application), or any other unanticipated serious problem associated with a device that relates to the rights, safety, or welfare of subjects.”

### 8.2 CLASSIFICATION OF AN EVENT

#### 8.2.1 SEVERITY OF EVENT

Each adverse event should be assessed for its severity, or the intensity of an event experienced by the subject, using the following classifications:

- **Mild:** easily tolerated by the subject, causing minimal discomfort and not interfering with everyday activities. These events generally do not require treatment.
- **Moderate:** sufficiently discomforting to interfere with normal everyday activities. These events are usually relieved by simple therapeutic measures.
- **Severe:** prevents normal, everyday activities. These events may require systemic drug therapy or other medical treatment.

#### 8.2.2 RELATIONSHIP TO THE INVESTIGATIONAL DEVICE

The investigators should differentiate between device and procedure related AEs by classifying events directly attributable to the device itself as “device related” and events that occur from the procedure, irrespective of the device, as “procedure related”. Since the study device delivers helium-based plasma energy to the tissue, events directly attributable to the application of energy to the tissue (i.e. burns) or the use of helium (i.e. gas buildup) should be classified as device related. Events that are known to occur in subdermal procedures utilizing tumescent anesthesia and/or undermining of soft tissue (i.e. edema, hematoma, nerve injury, pain/tenderness) without the use of the study device should be classified as procedure related.

The relationship to the study device and/or procedure will be determined by the investigator utilizing the following categories:

- Not Related: An event for which an alternative explanation is conclusively identified – e.g., concomitant drug(s), concomitant disease(s), and/or the relationship in time suggests that a causal relationship is highly unlikely.
- Related: The adverse event follows a reasonable temporal sequence related to treatment by the device and/or study procedure, follows a known or suspected response pattern and a plausible alternative etiology cannot be identified.
- Undetermined: The relation of the adverse event has some temporal relationship to the device and/or study procedure, is not clearly due to another condition and the involvement of the study device is unknown.

The investigator should assess the relationship of the adverse event to the investigational device. The relationship should be assessed using the categories presented in **Table 6**.

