## PROTOCOL SYNOPSIS

Protocol Title:	A Pilot Study of the Renuvion APR System when Used as an Adjunct Procedure in Gynecomastia Surgery
Investigational Device:	The Renuvion APR Handpiece (K191542) is a sterile, single use electrosurgical (monopolar) device intended to be used in conjunction with compatible generators for the percutaneous delivery of radiofrequency energy and/or helium plasma for cutting, coagulation and ablation of soft tissue. The Renuvion APR Handpiece is compatible with the Electrosurgical Generators BVX-200H/P (K170188), and APYX-JS3/RS3 (K192867) owned by Apyx Medical that are indicated for delivery of radiofrequency energy and/or helium gas plasma to cut, coagulate, and ablate soft tissue during open and laparoscopic surgical procedures.
Development Phase:	Pilot
Study Purpose:	To evaluate the use and safety of the Renuvion APR System as an adjunct procedure to bilateral gynecomastia surgery.
Brief Study Overview:	
This is a prospective, multi-center, single-blinded, randomized study of up to 10 study subjects undergoing bilateral gynecomastia surgery with Renuvion APR System used as an adjunct procedure on one side. The study will be conducted at up to 3 investigational centers in the United States.
 
At baseline, the grade of gynecomastia will be recorded by side, male chest measurements will be taken, and pre-surgery photographs taken in the frontal, lateral, and oblique views.
 
The gynecomastia surgery and Renuvion APR System use will be as per investigator's standard clinical practice. During the procedure, fat transfer and treatment of the lateral chest and/or axilla is not allowed. The Renuvion APR System will be used on one side only. The treated side will be randomized and the patient will be blinded as to which side of the chest received Renuvion. Procedure data and adverse events will be captured. Endermology is not allowed post-procedure. Post-procedure compression will be used for 2-3 weeks with a standard compression vest for all subjects.
 
Follow-up images, grade of gynecomastia, and male chest measurements will be taken at D30/D90/D180.
 
All images will be assessed for correct identification of Renuvion-treated side by blinded Independent Photographic Reviewers (IPR) following the D180 visit.
 
Following study participation, the subject will be offered an optional balancing treatment to the side not previously treated with Renuvion.

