## 7.2 STUDY PROCEDURE

The bilateral gynecomastia surgery and Renuvion APR System use will be as per investigator's standard clinical practice. During the procedure, fat transfer and treatment of the lateral chest and/or axilla is not allowed. The Renuvion APR System will be used on one side only, and alternate consecutively between patients, starting on the right side. For example, subject 001 will be treated with Renuvion on the right side, subject 002, will be treated on the left, subject 003 will be treated on the right, etc. This treatment scheme will continue until enrollment has completed at each site. The subjects will be blinded as to which side has been treated with Renuvion.

Procedure data and adverse events will be captured.

Endermology is not allowed post-procedure for the duration of the study.

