### 8.5 STUDY HALTING RULES

This clinical trial will be halted if subjects' safety is questioned based on a reporting of severe, device-related AEs at an excessive frequency. The Sponsor and/or investigator may recommend termination or modification of the study if there is an occurrence of any device- or treatment-related Serious Adverse Event, using the clinical protocol definitions of Serious Adverse Event. In addition, termination or modification may be recommended for any other perceived safety concern based on clinical judgment, including but not limited to a severe burn (anticipated or unanticipated), a higher than anticipated rate for any component of the safety measures, device failures resulting in Adverse Events, or unexpected SAEs. The study sponsor will notify all investigators to immediately halt any

continuing enrollment activities and not enroll any additional study participants. The study sponsor will inform the IRB/FDA of the temporary halt and the disposition of the study.

The Sponsor and/or investigator may recommend termination or modification of the study if there is an occurrence of any device- or treatment-related Serious Adverse Event, using the clinical protocol definitions of Serious Adverse Event. In addition, termination or modification may be recommended for any other perceived safety concern based on clinical judgment, including but not limited to a severe burn (anticipated or unanticipated), a higher than anticipated rate for any component of the safety measures, device failures resulting in Adverse Events, or unexpected SAEs. Enrollment and treatment would be suspended during root cause investigation to determine the cause of the respective AE.

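### Section 8.2.2 biases the device-related label downward for adverse events that the concurrent surgery can also cause

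*Protocol*

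**What the plan says.** The Synopsis describes subjects "undergoing bilateral gynecomastia surgery with Renuvion APR System used as an adjunct procedure on one side", and section 7.2 repeats that "The Renuvion APR System will be used on one side only". Each subject therefore has one side with surgery plus device and one side with surgery alone.

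Section 4.3.3.8 has the investigator rate device causality and procedure causality as two items, each on three levels. Section 8.2.2 defines the levels:

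- **Related:** "The adverse event follows a reasonable temporal sequence related to treatment by the device and/or study procedure", and it also "follows a known or suspected response pattern and a plausible alternative etiology cannot be identified".
- **Not Related:** "An event for which an alternative explanation is conclusively identified", or the timing makes causation highly unlikely.
- **Undetermined:** there is some temporal relationship, but the event "is not clearly due to another condition and the involvement of the study device is unknown".

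The same section tells investigators to separate device events from procedure events. Burns, as energy effects, and events from "the use of helium (i.e. gas buildup) should be classified as device related". Events known from subdermal procedures without the device (edema, hematoma, nerve injury, pain or tenderness) are assigned to the procedure. The section then also requires the five-level Table 6.

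Section 8.5 opens with a halt "based on a reporting of severe, device-related AEs at an excessive frequency". Sections 7.5.7 and 8.4.1 use the same device-related label for following events that are ongoing at the last visit.

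**The concern.** The device is never used without surgery at the same site in the same session. A causality rule that excludes 'Related' whenever another cause is plausible will therefore struggle to credit the device with any event that surgery can also produce, even one seen only on the Renuvion side. The operated control side is the natural evidence for separating the two causes, and 8.2.2 does not tell the investigator to weigh it.

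The study's purpose in section 3 includes safety, and its data may support a pivotal study. A low device-related count could then reflect the wording of the definition rather than what happened to the treated sides, and the same label feeds the first halting criterion.

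**Working it through.** The protocol states no event rate, so there is no figure of its own to reproduce. The check sets the texts side by side. The inputs are the design (Synopsis, 7.2), the two causality items (4.3.3.8), the definitions and assignment sentences (8.2.2), Table 6, the risk list (2.2.1) and the places that use the label (8.5, 7.5.7, 8.4.1). The test case is a seroma on the Renuvion side only.

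1. **Three-level scale, rated for the device alone** (as the separate item in 4.3.3.8 implies). 'Related' fails, because surgery is a plausible alternative cause. 'Not Related' also fails, unless that cause is conclusive or the timing rules the device out. The event becomes 'Undetermined'. Infection, fibrosis and induration, all listed in 2.2.1, go the same way.

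2. **Three-level scale, rated for device and/or procedure** (as the definition is worded). The seroma can be 'Related', but the label no longer says to which. That defeats the separate items in 4.3.3.8 and the instruction in 8.2.2 to differentiate.

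3. **Table 6.** 'Probably Related' and 'Possibly Related' do not require other causes to be excluded, so the seroma can be placed there. However, the rows speak of device and procedure together, and nothing maps the five levels to the three.

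4. **Assignment sentence against the risk list.** For four event types, 8.2.2 settles the matter before the definition is reached:

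| Event | 8.2.2 | 2.2.1 |
|---|---|---|
| Hematoma | procedure | risk of Renuvion treatment |
| Nerve injury | procedure | motor: risk of Renuvion treatment; temporary sensory: expected effect of energy-based treatment |
| Edema, pain | procedure | expected effects of energy-based treatment |

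No exception is made for an event that is absent or milder on the control side.

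5. **Use of the label.** Neither 8.5 nor the follow-up text in 7.5.7 and 8.4.1 says whether 'Undetermined' counts as device-related.

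6. **Size.** Let k be the number of Renuvion sides with a shared event of the kind in step 1, with k from 0 to 10. On the device-only reading, the device-related count is 0 if only 'Related' counts, and k if 'Undetermined' is added. As an illustration with assumed counts, take seroma on 3 of 10 Renuvion sides and 1 of 10 control sides:
   - Side difference: 3 − 1 = 2.
   - 'Related' only: 0.
   - 'Related' plus 'Undetermined': 0 + 3 = 3, which exceeds the side difference by 3 − 2 = 1.

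   The narrow count misses the excess, and the pooled count overshoots it. Only the comparison of sides shows it directly.

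**The case against.** A reader might infer that almost nothing except burns and gas buildup can ever be called device-related, that the count is forced to zero on any scale, and that the halting rule is therefore blind. The documents do not support this:

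- The 'Related' definition names device and/or procedure. The result in step 1 needs the device-only reading, and even there the event becomes 'Undetermined', not unrelated.
- Table 6 allows a rating of possible or probable without excluding other causes.
- Burns and gas buildup stand for energy effects and helium effects. Helium embolism, listed in 2.2.1, could also qualify.
- Plausibility is the investigator's judgement, and nothing forbids looking at the control side.
- The primary safety endpoint (4.3.1) is adverse event occurrence on both sides without regard to cause, so an imbalance stays visible.
- Section 8.5 also allows action on treatment-related serious events and on any perceived safety concern.
- Section 8.3 says, without an attribution condition, that events are followed to resolution or stabilization. This softens the follow-up consequence.
- How categories are pooled in tables is commonly left to the SAP, which is not shown.

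All of this stands and limits the point. It does not remove it. The joint reading and Table 6 reach 'Related' only by merging the two causes that 4.3.3.8 and 8.2.2 ask to be kept apart. The assignment sentence carries no exception, and its conflict with 2.2.1 remains. What 'device-related' means in the first halting criterion is for the protocol to settle.

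**Conclusion.** The concern holds in a limited form. For events that surgery can also cause, the attribution rules in 8.2.2 push the device label downward: some events go to 'Undetermined' by definition, and four named types go to the procedure by instruction. Two unreconciled scales, and the conflict between 8.2.2 and 2.2.1, add to this.

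The conclusion assumes that the device item is rated for the device alone and that investigators regard the concurrent surgery as a plausible cause. The extent is unknown, because no event rates are given. The bounds of 0 and k in the working are all that can be said. The side comparison in the primary endpoint is not affected, and the halting rule is weakened in its first criterion rather than disabled. The wording should be corrected, but the point does not undermine the trial.

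**What to change.** 1. Amend 8.2.2, including the assignment sentence, so that the concurrent surgery by itself does not rule out a device relationship, and so that the investigator must weigh whether the event is absent or milder on the control side.
2. Name one causality scale and apply it separately to device and procedure. Reconcile 4.3.3.8, the three levels in 8.2.2 and Table 6 with each other, and 8.2.2 with the risk list in 2.2.1.
3. In device-safety summaries, count 'Undetermined' together with 'Related'. Present the primary endpoint as Renuvion-side versus control-side occurrence regardless of label. This needs the affected side on the event form, which the list of collected items in 8.3 does not name.
4. Reconcile 7.5.7, 8.4.1 and 8.5 with the chosen definition of device-related, stating how 'Undetermined' counts. What the halting criterion itself should be is for the sponsor and is not proposed here.

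The cost is some wording and one safety table. The downside is a higher, more conservative device-related count, which will include some surgical events that fell on the Renuvion side by chance.
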